Power. In repeated-measures studies, both the number of waves of data per individual (e.g. level-1 units) and the number of persons (i.e., level-2 units) affect the power to detect various effects. In cases where the within person variance is large relative to the between-person variance of the growth rate and persons vary in their growth rates, the total sample size is less important in determining power than either the

frequency of the observations or the duration of the study. Using a formula provided by Raudenbush and Bryk (2001), investigators calculate that, given 6 time points spaced over 9 months, a sample size of a minimum 135 will be large enough to detect moderate effects in change rates. Using Optimal Design, a program used for multilevel modeling, to get an unstandardized effect size of .035, investigators would need a conservative estimate of 135 repeated measures of participants in each condition to obtain .8 power to detect between person differences. The effect size is based on the difference in slopes (change rate) between differences (e.g., people with high versus low dose; level of cross-sector collaboration; formal or informal social role). The total sample is 450 participants (50 participants per villages, 9 villages), and a conservative estimate of 135 participants with high dosage (3+ LCs), half the villages with 3+ sectors attending, and a third of the participants in formal roles.

Aim 2: Document the community-level impact of PC CARES by tracking the number and type of interactions aimed at preventing youth suicide and promoting wellness in participating villages, and describe changes in the supportive social networks of young people before and after the intervention.

Overview. Investigators will record the effectiveness of the intervention at the network and community level by performing pre- and post-intervention network interviews documenting the level and type of institutional/role interactions that take place across those institutions and the social positions best able to meet the needs of young people at risk for suicide. Ideally, these communities could be sorted into case and control groups.

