Given that this study will not have a comparison group, the study is designed to test for significant *within-person* changes in the study outcomes (PC CARES). Investigators will guard against potential ordering effects by randomly selecting which of the 15 eligible villages will be invited in Cohort 1, 2, or 3. The design choice to include staggered starts for the 3 intervention cohorts allows us to guard against the possibility that a single external event could explain the results (Rhoda, Murray, Andridge, Pennell, & Hade, 2011).

In addition, the staggered treatment starts will provide three distinct replications of the intervention. Based on the methodological suggestions provided, investigators will examine within-person effects in each of the 3 cohorts of 150 participants, rather than pooling across the 3 cohorts as proposed in the initial analysis plan.

Section B. History and rationale for not including a comparison group.

Doing research in rural Alaska Native communities, particularly about the significant health disparity of youth suicide, requires a high level of sensitivity, community involvement and shared decision-making. These research values are particularly important given the history of maltreatment and exploitation related to research in many tribal communities (Wallerstein & Duran, 2010; Caldwell, et. al., 2005; Norton, & Manson, 1996), and specifically in Alaska Native communities (Rivkin, et. al., 2013; Foulks, 1989). Consequently, there is a pervasive mistrust and suspicion of research in Indigenous communities across the U.S. Having done tribal community-based participatory research in rural Alaska Native communities for over 20 years, the PI ([name]) understands how to balance scientific and community priorities in respectful ways.

[figure not shown]

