Though the original study design was powered to examine within-person change in study outcomes, the initial analysis plan proposed to examine within-person change pooling participants across the 3 study cohorts (150 participants each, for a total sample size of 450). In the original power analysis using Optimal Design software (Raudenbush et Liu, 2001), investigators chose to model a moderate effect size, which was the unstandardized coefficient relating time to the outcome. In other words, it is the expected rate of linear change per unit time in an unstandardized metric. So, an effect size of .08 means that the study is powered to find a positive growth rate of .08 units per session. This curve (Figure 1) is generated by the multilevel power program Optimal Design (Raudenbush et Liu, 2001) and shows the power curve to detect linear change. It is based on the following parameters: 6 repeated measures, alpha set to .05, a ratio of between-person to within-person variance of 3:1, and an unstandardized effect size of .08.

Given these parameters, the study would need 150 participants to detect an individual difference (such as hypothesized dosage or role effects) of .08 on the slope of linear change in the study outcomes. Thus, with cohorts of 150 participants each, the study is sufficiently powered to detect the expected effects on within-person change for each cohort. In addition to analyzing change within each cohort separately, investigators will use descriptive statistics to compare the findings across the 3 cohorts to

explore whether consistencies are present that might be indicative of a treatment effect.

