Investigators have re-done the power analysis using a Monte Carlo simulation method with the MPlus software package (Muthén & Muthén, 2002). This calculation is based on pilot data from the R34 MH096884, which was unavailable at the time of the original submission. The effect sizes for within-person change have been estimated from the pilot data rather than assumed (as was the case with Optimal Design). The investigators acknowledge that the original analysis plan neglected potential cohort effects of time (e.g., historical external events), and agree with the reviewer's suggestion that the study focus on each cohort separately in all analyses. In response to these methodological concerns about pooling the groups, investigators have conducted power analyses at the cohort level to test for within-person change. As results indicate, the analyses showed that the study will be sufficiently powered to detect effects at the cohort level (per cohort of 150 participants).

As described, since the time of the original proposal investigators have completed data collection and cleaning, thus enabling us to use pilot data in the power analysis calculations. This pilot study used the same outcome measures and the same intervention as proposed in the present work. Using pilot data in power calculations provides more accurate estimates for statistical power than formula-based approaches; this issue is particularly important in estimating power for multilevel models, where multiple parameter estimates for both fixed and random effects must be known in order to make obtain power calculations (Bolger & Laurenceau, 2013).

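### The stated power for dosage and role effects does not carry over to the cohort-by-cohort analysis, and 135 high-dosage participants is a best case on the SAP's own attendance figures

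*SAP*

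**What the plan says.** SAP Aim 1, Power, sizes the comparison of slopes between groups (high v low dosage, level of cross-sector participation, formal v informal role). It first says that "a sample size of a minimum 135 will be large enough to detect moderate effects in change rates" and then, for an unstandardized difference of .035, that "investigators would need a conservative estimate of 135 repeated measures of participants in each condition to obtain .8 power to detect between person differences". Against this it sets a pooled sample of 450, "a conservative estimate of 135 participants with high dosage (3+ LCs"), and a third of participants in formal roles.

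Section A changes the unit of analysis: "investigators will examine within-person effects in each of the 3 cohorts of 150 participants, rather than pooling across the 3 cohorts". Section C accepts the advice "that the study focus on each cohort separately in all analyses".

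Section C also recounts the Optimal Design calculation, now with .08. It defines that figure as mean growth ("it is the expected rate of linear change per unit time in an unstandardized metric"), lists among its inputs "a ratio of between-person to within-person variance of 3:1, and an unstandardized effect size of .08", and then says that "the study would need 150 participants to detect an individual difference (such as hypothesized dosage or role effects) of .08 on the slope". The Monte Carlo work that follows reports, in Table 1, power for average linear change and for the variance of the slopes. Moderator tests stay in the plan, restricted to knowledge and skills. The Data Analysis section of the 2023 combined document still names dosage and social role as factors to be examined.

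Aim 1, Participant recruitment, expects 15–20 people at each of four circles and at least 50 distinct people per village, and conservatively expects a third to attend most circles.

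**The concern.** Finding the factors that influence change is half of Aim 1. The Aim 1 power statement was built for one pooled sample and was not revised when the analysis moved to three cohorts. The Section C statement matches the cohort size, but carries a mean-growth effect over to a difference between groups without saying how the groups are split. If neither gives usable power for a dosage or role effect in a cohort of 150, a null moderator result in a cohort cannot be interpreted.

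The high-dosage head count matters for the same reason. It fixes the smaller group in the dosage comparison, and power falls as that group shrinks.

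**Working it through.** **Inputs.** Aim 1, Power: difference .035, 135 per condition, power .8; 135 of 450 high dosage; a third formal. Section C: difference .08, 150 participants, six waves, alpha .05. Cohort size 150 (Sections A and C). Divided over three cohorts, the expected splits are 45 v 105 (dosage) and 50 v 100 (role).

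**Method.** The absolute variances are not given, so neither N can be rebuilt from first principles. Each statement is instead calibrated to its own N (normal approximation, two-sided .05 assumed). With h = n1·n2/(n1 + n2), power = Φ(c·√(h/h0) − 1.96), where h0 belongs to the stated N and c = 2.80, 3.00 or 3.24 for 80, 85 or 90% base power.

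- 135 v 135: h0 = 67.5.
- 75 v 75: h0 = 37.5.
- 45 v 105: h = 31.5.
- 50 v 100: h = 33.3.

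**The Aim 1 statement as designed.** Pooled, 135 v 315 gives h = 94.5 and Φ(2.80·√(94.5/67.5) − 1.96) = 91%. The claim is coherent for a pooled sample.

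**The same statement per cohort.**

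- Dosage: Φ(2.80·√(31.5/67.5) − 1.96) = 48%.
- Role: Φ(2.80·√(33.3/67.5) − 1.96) = 50%.

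**The Section C statement per cohort (.08), if 150 was set at 75 v 75.**

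| Assumed power at 75 v 75 | Dosage 45 v 105 | Role 50 v 100 |
|---|---|---|
| 80% | 73% | 75% |
| 85% | 78% | 81% |
| 90% | 84% | 86% |

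To reach 80% at the expected splits, the 1:1 power must be at least 86% (dosage) or 84% (role).

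**Can .035 and .08 be compared?** The implied SD of a participant's estimated slope is effect·√h0/c. For .035 it is .035·√67.5/2.80 = .103. For .08 it is .08·√37.5/c = .175, .163 or .151 at 80, 85 or 90%. In a shared time unit these differ. If .035 is per month over nine months and .08 per session over five intervals (assumption), the whole-study effects are .315 and .40. The SDs are then .315·√67.5/2.80 = .92 and .40·√37.5/2.80 = .87, which nearly agree. The SAP gives no time unit for .035.

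**Attendance limit.** Each of 50 people uses one attendance, and each person at three or more circles uses at least two more. The maximum per village is therefore (attendances − 50)/2.

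| Circles × attendees | Attendances | Maximum per village | Nine villages |
|---|---|---|---|
| 4 × 15 | 60 | 5 | 45 |
| 4 × 17.5 | 70 | 10 | 90 |
| 4 × 20 | 80 | 15 | 135 |
| 5 × 15 | 75 | 12 | 108 |
| 5 × 20 | 100 | 25 | 225 |

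The figure of 135 is reached only with 20 people at every one of four circles, and with everyone attending either once or exactly three times. A third of 450 is 150, or 16.7 per village. That needs 33.3 × 1 + 16.7 × 3 = 83.3 attendances, or 20.8 per circle, above the stated range. At 15 per circle the best dosage split in a cohort is 15 v 135 (h = 13.5): 24% for .035 and 39% for .08 at 80% base power.

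**Missing surveys.** Post-surveys come only from attended circles. Even if everyone completes the pre-survey and follow-up, a village yields 50 + 50 + (60 to 80) = 160–180 of 300 surveys, so 40–47% are missing. The simulation assumes 30%. The power figures above assume complete waves and no village clustering.

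**The case against.** Five points on the other side deserve weight.

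- A reader might infer that .035 and .08 contradict each other outright. The documents do not support that. Under a month-versus-session reading they nearly agree. The power curve behind .08 is also in a figure that could not be read; if it showed about 99% power, the implied SD would be .08·√37.5/4.29 = .114, close to .103. What stands is that unit, split and power level are not in the readable text.
- Section C follows the Aim 1 paragraph and might be taken to supersede it. Then only the .08 statement counts, and on its own terms power is about 73–86%, around the usual 80%. That is fair, but it still depends on an unstated split, and the Aim 1 statement remains uncorrected.
- One Aim 1 sentence can be read as 135 in total. At 80% for 135 in equal halves (h0 = 33.75), a cohort would have 77% (dosage) and 79.5% (role). The sentence that states .8 power, however, says in each condition.
- Table 1 is offered as showing a precondition for moderation, namely that slopes vary. It is sound as that. It does not supply power for a moderator.
- The attendance limit rests on planning estimates. At the pilot's 47 per village (376/8), four circles of 20 allow 16 per village, or 144. The 2023 document plans at least nine villages, and its Data Analysis section counts five circles, though its Background still says four. The 135 may come from the SAP's 15 people per village with four or more surveys (15 × 9), and the third may refer only to people eligible for education credits. So 135 is not an absolute ceiling for the trial. It is still the top of the range on the SAP's own figures.

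**Conclusion.** The point holds as a should-fix correction to the moderator power statements. The 270 people implied by the Aim 1 paragraph cannot be found in a cohort of 150. On its calibration, per-cohort power at .035 is about 48% (dosage) and 50% (role). The Section C claim for .08 gives about 73% and 75% if 150 means 80% at equal groups, and meets 80% only if the 1:1 power was about 84–86% or more. These figures assume a two-sided .05 test, complete waves and no clustering. No passage reports power for a dosage or role effect from a model that contains one.

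The 135 high-dosage figure is the best case of a 45–135 range for four circles, 50 people per village and nine villages, so it is not conservative. With five circles the maximum is about 108–225.

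A reader might go further and conclude that Aim 1 as a whole is underpowered. The documents do not support that: Table 1 gives more than 99% power per cohort for mean change on three of four scales, and nothing here challenges it.

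**What to change.** 1. State one moderator effect with its time unit, variances, group split and power level, and use it in both Aim 1, Power, and Section C.
2. Replace the statement that 150 per cohort suffices for dosage and role effects. Extend the existing Monte Carlo simulation with a moderator-by-time term at 45 v 105 and 50 v 100, using the missing-survey pattern that attendance implies, and report that power per cohort.
3. Until this is done, label by-cohort moderator tests exploratory.
4. Drop the word conservative for the 135 high-dosage figure. Give the attendance-based range with its assumptions: 45–135 for four circles, about 108–225 for five.

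The cost is SAP wording and one extension of a simulation that already exists; no new data are needed. A pooled moderator model with cohort-by-time terms is an option for the investigators, not part of this correction. It would assume a common moderator effect across cohorts and depart from the decision to analyse cohorts separately.

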understanding of) the research; and a 3 indicates that research evidence was interpreted inaccurately, leading to conclusions inconsistent with its intent. A narrative rationale is provided for each score. Investigators use both reviewers' ratings to calculate an average. In the pilot, with 35 LCs currently coded, there is a high level of accuracy, average of 1.21. Investigators consider scores under 1.5 to be adequate accuracy. If scores fall above this threshold, investigators will work with facilitators to improve their understanding of the research. *Fidelity.* Investigators assess fidelity for each of the 6 standard elements of each LC: (1) agreements/safe talk, (2) small wins, (3) the LC activity, (4) what we know, (5) what we think, and (6) what we want to do. Each dimension gets 0-1 for procedural components (i.e., presenting specific data, giving clear instructions to the group) that are present (1), absent (0), or not captured (NA) on the recording when the audio clearly misses some of the LC. Investigators will average these scores across two raters for each element, consider scores for each LC, and for each community, providing clues to decipher issues in a particular element, LC, or village, so it can be addressed. Pilot fidelity scores average .79 across two raters, indicating acceptable adherence to the curriculum.

(4) Measure PC CARES participants' knowledge, attitudes and behavior over time.

Participant recruitment: Based on the pilot study, investigators estimate 15-20 participants in each of 4 LCs and at least 50 distinct participants per village. The pilot study shows this is feasible with 376 participants attending LCs in 8 villages with less follow-up and support. With 3 villages per cohort, investigators estimate 150 people per cohort who attended at least 1 LC, with a total number of participants across 3 cohorts at 450. Investigators believe that those who are eligible to receive CEUs will be most likely to come to 3+ LCs and conservatively estimate a third will attend most LCs. For follow-up, investigators will invite all participants to complete the follow-up survey 3 months after the last LC. The research team will stop trying to contact participants after three attempts, and aim to have at least 25 (50%) of the follow-up surveys completed per village (Total=225). This level of recruitment was more than achieved in the pilot (65%) by working with local facilitators to find individuals and send the surveys back to UMass.

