As a reference point, investigators will first report the analyses from the pilot data collection for each of the primary outcome scales of the PC CARES measure related to the primary and secondary suicide prevention intervention. These 4 outcome scales are: suicidal prevention *knowledge, skills* related to handling suicidal behavior, *community of practice* to respond to suicide risk and suicidal behavior, and *intention to act* regarding suicide prevention. In the pilot data collection, only 2 assessments were collected for most participants: pre-intervention and follow-up. In order to provide a sense of the magnitude of the intervention effects, paired samples *t* tests were conducted to estimate within-person change as a difference score in these outcomes pre- to post-intervention. Results showed statistically significant increases of moderate effect size in three of the four primary outcome measures. This difference can be converted to an effect size (Morris & DeShon, 2002), which account for the correlation between the two scores. For the 82 participants with complete pilot data pre- and post- intervention: significant increases were found in the suicide prevention knowledge scale (increase from 3.27 (.77) to 3.84 (.61), ES: .69) (Morris & DeShon, 2002), the skills to handle risk and suicidal behavior scale (increase from 3.64(.80) to 4.05(.68), ES= .49), and the community of practice in response to suicidality scale (increase from 3.52(.81) to 3.90(.78), ES= .43). The increase in the intention to act subscale was not statistically significant and much smaller in effect (increase from 3.84(.59) to 3.91(.60), ES = .12). Investigators believe that the within-person changes to the 'intention to act' is not significantly higher in PC CARES participants because those who voluntarily participate in the intervention are already highly motivated to take prevention action. Indeed, by attending the PC CARES intervention, they are taking action for prevention in their home communities. The ceiling effect is expected.

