Where *Outcome* is one of the primary suicidality knowledge outcomes: suicidal prevention *knowledge*, *skills* related to handling suicidal behavior, *community of practice* to respond to suicide risk and suicidal behavior, and *intention to act* regarding suicide prevention. *Time0to1* represents the repeated measures within individuals over the course of the intervention, rescaled so that a one unit change in *Time0to1* represents participant linear change in the outcome from baseline to follow-up.

Investigators used guidelines for conducting power analyses via Monte Carlo simulations for multilevel models (Bolger & Laurenceau, 2013, Gelman & Hill, 2006) with Mplus statistical software (Muthén & Muthén, 1998–2012, 2002). In this technique, parameter estimates obtained from a linear growth curve model of the pilot data are used as population estimates, and multiple simulation studies for the specified sample size are conducted from this population. Across simulations, investigators calculate the percentage of times any given parameter estimate was statistically significant. In general, 80% power to detect effects is considered to demonstrate sufficient power.

Recently-completed analyses from the pilot study are the basis for the current calculations. Investigators conducted post hoc power analyses using the same sample size and missingness patterns as the pilot sample, in order to obtain an estimate of the fixed and random effects for change in each outcome found in the pilot study. Next, investigators conducted power analyses for the expected size of each cohort in the new study and the proposed number of repeated measurements: 150 individuals with 6 repeated measures, assuming 30% missing data. Following recommendations, 1,000 simulations were conducted to obtain estimated power to detect effects (Bolger & Laurenceau, 2013). Results are summarized in Table 1, next page. Within-person linear change was found to be sufficiently powered, even in the pilot sample, for the first three outcomes. Consistent with pre-post analyses of the pilot data, the smaller sized within-person change in the intention to act scale was underpowered in the original sample size, as was its random effect. Thus, investigators find evidence that the primary

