Youth suicide continues to disproportionately affect Indigenous communities, and has been difficult to detect early, prevent and reduce. In rural Indigenous communities, youth suicide is an extreme health disparity with Alaska Native (AN) suicide rates in remote villages up to 18 times higher than the rates of all American youth, ages 15-24 (124 vs 6.9 per 100,000). AN youth who are showing signs of vulnerability but are not yet suicidal, are likely to interact with a variety of community workers such as village public safety officers, health aids, and school personnel. In 62% of all suicidal behavior in Northwest Alaska (NWA), AN youth display distress to their family and friends. A local survey (n=355) also revealed AN youth sought help from peers (54%), parents (40%), grandparents/Elders (21%), uncles/aunts and teachers (20%). These supporters, however, are not prepared to recognize suicide risk or reduce it before an acute event, when there are more options for culturally-responsive, social care (i.e. Elder mentoring, cultural activities) and risk reduction (i.e. removing guns from the home). Now, 75% of all suicide interventions in NWA are 'imminent risk' requiring safety protocols that forcibly remove distressed youth from their community (50+ air miles away) for hospital risk assessment, and return them 48 hours later even less likely to seek help the next time. There is a clear need for 'upstream' suicide prevention before a crisis, which activates a youth's social network, reduces suicide risk and increases resources for wellness in rural AN communities. Representing a culmination of 20 years of community-based participatory suicide prevention research, Promoting Community Conversations About Research to End Suicide (PC CARES), does just that. It is built on the notion that community members are cultural and community experts, who are in the best position to create working solutions to their health problems, and recognizes that scientific knowledge can guide these efforts to strategic benefit. With strong tribal support and evidence of feasibility from the pilot study from 2014- 2017, the model has local facilitators host four 3-hour learning circles, where family members, youth, and village providers learn about prevention science, and adapt and apply it to their local and cultural realities. Demonstrating potential for changing participants' knowledge and attitudes in rural Alaska, this trial will assess the transferability and preliminary effectiveness of PC CARES on individual and community levels.

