Using a multi-level growth model for participant outcomes, we will generate reliable estimates of changes in participants' knowledge, attitudes and behaviors before, over our 4-6-month intervention and follow-up: 7 occasions of measurement (Baseline STP survey, 5 Learning Circle surveys completed after each learning circle and a Follow-Up STP survey). We will model variability in these changes over time, and identify key factors affecting these outcomes within the three domains identified through our pilot study: a) cross-sector participation on a community level; b) individual dosage, and c) participant social role: informal or formal. In addition, we will record the effectiveness of our intervention at the network and community level by performing pre- and post-intervention Steps Toward Prevention surveys documenting the level and type of institutional/role interactions that take place across those institutions and the social positions best able to meet the needs of young people at risk for suicide. Pre-post intervention STP surveys and variation in initial rollout timing will create a natural stepped wedge design. To assess intervention outcomes we will collect bipartite (individual and institution/social role) interaction data in each participating community. This method builds on research previously undertaken by the research team in NWA in 2015-17 and Inuit communities in Arctic Canada in 2010-11, and will focus on levels of cross-sector collaboration (including informal supports) and youth support networks within each community. Rigorous network statistical analyses will focus on variation across participating communities, and before/after the community-level intervention. Structural clustering of 12 family and community level network roles and key organizations will be derived via the 1) transformation of bipartite graphs of individuals and organizations/roles in single-mode, sector-level social networks with interaction weighted links, 2) use of Generalized Ward's criterion to discover meaningful clusters of structured interaction, and 3) block modeling of these clusters (using standard density criterion) to create models of organizational structure. Analysis of the pre- and post-PC CARES structures will allow us to capture changes in suicide prevention and supportive practices within and between these network roles/organizations before and after each cohort wave of 3 villages, and across all the intervention villages.

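### Table 1 assumes 30% missing surveys, but the SAP's own recruitment targets imply 48–55%; and two general power statements pass over intention to act, printed at 59.4%

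*SAP*

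**What the plan says.** The SAP makes four statements that bear on this point.

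- **Simulation (Section C, text before Table 1).** Power per cohort is for "150 individuals with 6 repeated measures, assuming 30% missing data". Power of 80% is the criterion for sufficiency.
- **Attendance (Aim 1, Participant recruitment).** "investigators estimate 15-20 participants in each of 4 LCs and at least 50 distinct participants per village". For follow-up, the team will "aim to have at least 25 (50%) of the follow-up surveys completed per village"; the pilot is said to have reached 65%. A post-survey is given after each circle, and the Missing data paragraph counts circles not attended as missing waves.
- **Dosage (Aim 1, Power).** Of 450 people, the SAP gives "a conservative estimate of 135 participants with high dosage (3+ LCs"), which is 15 of 50 per village.
- **Intention to act (Section C).** This is one of four primary scales. Its pilot change was "much smaller in effect (increase from 3.84(.59) to 3.91(.60), ES = .12"). Table 1 prints 21.6% power for the pilot sample and 59.4% for N=150. The text says "the smaller sized within-person change in the intention to act scale was underpowered in the original sample size". The next sentence limits its claim of sufficient power to knowledge, skills and community of practice. But the introduction to the Monte Carlo work, and the sentence directly after Table 1, call each cohort sufficiently powered with no scale excepted.

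**The concern.** Table 1 is the justification for analysing each cohort separately instead of pooling. Its missing-data input is given no source and does not agree with the attendance and follow-up targets a few pages earlier. The fixed-effect powers and the random-effect powers (99.5% and 99.6%) that led to moderator analyses of knowledge and skills only were all computed under that input.

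The second problem needs no modelling. A reader who takes the summary sentences at face value will think all four primary scales are adequately powered per cohort. Because the text calls intention to act underpowered only at the pilot's size, it suggests that N=150 cures this. Table 1 shows that it does not. A non-significant result on that scale in one cohort could then be read as no change.

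**Working it through.** **1. The plan's own figure.** The growth-model estimates behind Table 1 are not printed, so 59.4% cannot be reproduced strictly. A shortcut from the pilot effect size gives 0.12 × √94 = 1.163, or 21.4% power (two-sided 5%), close to the printed 21.6%. The same shortcut gives 99.7% for skills (printed 94.7%) and 98.6% for community of practice (printed 91.3%), so it does not represent the SAP's model. Scaling intention to act from 21.6% to N=150 gives 27–31% at 30% missing. The 59.4% is therefore unexplained, but not shown to be wrong.

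**2. Missing share per village.** Possible surveys: 50 people × 6 = 300. Missing = 1 − (50 pre-surveys + 4 × attendance per circle + follow-ups)/300.

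| Attendance per circle | 25 follow-ups (50%) | 32.5 (65%) | 50 (100%) |
|---|---|---|---|
| 15 | 1 − 135/300 = 55.0% | 1 − 142.5/300 = 52.5% | 1 − 160/300 = 46.7% |
| 20 | 1 − 155/300 = 48.3% | 1 − 162.5/300 = 45.8% | 1 − 180/300 = 40.0% |

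These counts credit everyone with a pre-survey and every attendee with a post-survey. Thirty percent missing means 0.7 × 6 = 4.2 surveys per person; the targets give 135/50 = 2.7 to 155/50 = 3.1. Reaching 210 surveys needs (210 − 75)/4 ≈ 34 people per circle at 50% follow-up, or (210 − 100)/4 = 27.5 at full follow-up.

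**3. The dosage statement.** If 15 of 50 attend at least three circles and the other 35 attend one or two, attendances run from 15×3 + 35×1 = 80 to 15×4 + 35×2 = 130.

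- With the 15–20 limit: 20 per circle gives exactly 80 attendances. At 15 per circle there are 60, only 10 beyond one each, so at most 10/2 = 5 people can reach three.
- Without the limit, at 50% follow-up: 1 − 155/300 = 48.3% down to 1 − 205/300 = 31.7% missing. The lower end needs 130/4 = 32.5 people per circle.

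**4. Effect on intention to act, taking the printed 59.4% as correct at 30% missing at random.** A power of 59.4% corresponds to z = 1.960 + 0.238 = 2.198. Under another pattern, power ≈ Φ(2.198 × √R − 1.960). R is the expected information on the linear slope relative to 30% random missingness, in the SAP's random intercept and slope model. Assumed ranges: intercept variance 0.5–3 and slope variance 0–1 (residual variance 1), with several wave spacings.

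| Pattern | R | Power |
|---|---|---|
| Planned attendance, 50% follow-up (48–55% missing) | 0.72–0.88 | 46–54% |
| Same share missing evenly across waves | 0.51–0.76 | 35–48% |
| Planned attendance, full follow-up (40–47% missing) | 1.11–1.37 | 64–73% |

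The limits move by a few points with the assumed spacing. Follow-up of 65% falls between the first and third rows. Reaching 80% would need R = (2.802/2.198)² ≈ 1.6.

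**5. The other scales.** Calibrated to the pilot column of Table 1, mean-change power under planned attendance with 50% follow-up is about 95–98% for skills and 92–97% for community of practice. Knowledge has a larger effect. The random-effect powers cannot be rechecked without the variance estimates.

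**The case against.** The best defence is that the gap changes no decision. Intention to act is already printed below 80%, and the other three scales stay above it under the planned attendance. That is right, and it limits the weight of the point; it does not make the input correct.

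Second, the disclosure is better than the two summary sentences suggest. One sentence restricts the claim to three scales, Table 1 prints 59.4% beside an 80% note, and the SAP says a ceiling effect is expected. This also stands: the fault is two over-broad sentences, not concealment.

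Third, 48–55% is not the only figure the SAP supports. The dosage estimate alone allows about 32% at 50% follow-up, and 1 − 212.5/300 = 29.2% at 65%. That is a fair objection, but it requires dropping the 15–20 attendance figure.

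A reader might infer more than the documents support:

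- *That true power for intention to act is only 22–48%.* Such figures come from scaling the pilot column, which discards the printed 59.4% without showing it to be wrong.
- *That 40% missing with full follow-up is worse than 30% missing at random.* It carries more slope information, because the first and last waves are complete. The pattern matters as well as the percentage.
- *That the 2023 protocol makes Table 1 wrong.* That protocol describes "7 occasions of measurement (Baseline STP survey, 5 Learning Circle surveys completed after each learning circle and a Follow-Up STP survey"), while its Background says "the model has local facilitators host four 3-hour learning circles". The two must be reconciled, but this is a separate matter and cannot be an error in a 2018 simulation.

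**Conclusion.** The point holds on two counts. The 30% missing-data input disagrees with the SAP's recruitment targets, which imply 48–55% (46–53% at 65% follow-up), and the two attendance statements agree only at 20 people per circle. Separately, the unqualified power statements are contradicted by Table 1 for one of four primary scales, which is 80 − 59.4 = 20.6 points short as printed.

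The practical size is modest. Intention to act is below 80% in every pattern examined, and mean-change conclusions for knowledge, skills and community of practice are expected to stand. The missing shares are direct counts from stated targets, some of which are floors. The power ranges are approximate: they rest on the printed 59.4%, a two-sided 5% test, and assumed variances and wave times.

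**What to change.** 1. Reconcile the attendance figures in the Participant recruitment and Power paragraphs of Aim 1.
2. Re-run the existing simulation with post-surveys only for circles attended and 50% follow-up, with 65% and full follow-up as labelled sensitivity cases. Restate the fixed- and random-effect entries in Table 1, and report the pilot estimates and wave times used.
3. Qualify the sentence introducing the Monte Carlo work and the one after Table 1, for example:

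> With cohorts of 150, mean change in knowledge, skills and community of practice is sufficiently powered in each cohort; mean change in intention to act is not, and a non-significant result on it in one cohort will not be read as no change.

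The wording after Table 1 also appears earlier in Section C for the Optimal Design calculation and should be kept consistent.

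The cost is one re-run and a few edited sentences, with no added enrolment or data collection. The downside is slightly less favourable stated figures.
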